### 10.3 Exploratory Outcome Measures

- HRQOL in Appendices (B-H) will be collected by paper or electronically by the research coordinator at every study assessment visit or via mail or the myHealth messaging system (see Study Calendar). Data will be collected and stored in RedCap. Patients will receive 5 surveys (tailored to patient gender and the presence of a stoma). The entire functional assessment can be completed in less than 30 minutes, with an average of 15-20 minutes per patient.
  - Bowel function index (BFI)
    - We will use the 19-item BFI to assess bowel function. The psychometric properties of the instrument have been previously published and all subscales and total score show good internal consistency.
  - Low Anterior Resection Score (LARS)
    - All patients without a stoma will also complete 5 additional questions from the LARS. This is a validated 5 question index that was specifically developed to categorize bowel dysfunction after low anterior resection. In the LARS Score patients are asked to describe symptoms which best describe daily life. There is no specific time period, but at most the averages are over the past week. The LARS score has a range of 0-42 with 0-20 being No LARS, 21-29 being Minor LARS, and 30-42 being Major LARS.
  - Stoma QOL
    - We will also use the 21-item Stoma QOL for patients undergoing APR.
  - Sexual function
    - To assess sexual function, we will use gender-specific questionnaires: 5-item International Index of Erectile Function (IIEF-5) and 6-item Female Sexual Functioning Index.
  - Bladder function
    - Bladder function will be assessed using the International Prostate Symptom Score.
  - EuroQOL Group five dimensions Health Questionnaire (EQ-5D)
    - The EQ-5D is a widely used descriptive system of HRQOL states. It consists of five dimensions (mobility, self-care, usual activities, pain/discomfort, anxiety/depression) each of which can take one of five responses. The responses record five levels of severity (no problems/ slight problems/ moderate problems/ severe problems/ extreme problems or unable to function) within a particular EQ5D dimension. The EQ5D is almost always combined with a simple linear analogue

scale that asks respondents to rate their overall health on a vertical scale of 0 to 100.

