### **12.5.2 Analysis Plan**

For the toxicity outcome, we will calculate the proportion of patients meeting our definition of toxicity. In addition, we will present the frequency and percent of other adverse events reported in the study.

Local regrowth rate will be calculated as the proportion of patients with local regrowth based on the secondary analysis population. The local regrowth rate and its 95% confidence interval will be calculated.

Disease-free survival is defined as the time from start of RT therapy to date of progression or death due to any cause. If a subject is not known to have progressed or died, then DFS will be censored at the latest date the subject was known to be alive or disease-free (on or before the cut-off date). The DFS distribution will be estimated using the Kaplan-Meier method, and the Kaplan-Meier curves, medians and 95% confidence intervals of the medians will be presented.

Colostomy-free survival distribution will be estimated using the Kaplan-Meier method, and the Kaplan-Meier curves, medians and 95% confidence intervals of the medians will be presented.

OS is defined as the time from start of RT therapy to date of death due to any cause. If a subject is not known to have died, then OS will be censored at the latest date the subject was known to be alive (on or before the study end date). The OS distribution will be estimated using the Kaplan-Meier method, and the Kaplan-Meier curves, medians and 95% confidence intervals of the medians will be presented.

For the HRQOL measures, we will calculate the mean and standard deviations of each of the individual indices at baseline and every 3 months during the duration of the study; we will graphically depict scores at each time point. In addition, we will calculate the difference of the QoL scores at the baseline, time of cCR, and last follow up date and report summary statistics.

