## Appendix E: International Index of Erectile Function (IIEF-5)

### The IIEF-5 Questionnaire (SHIM)

Please encircle the response that best describes you for the following five questions:

Over the past 6 months:					
1. How do you rate your confidence that you could get and keep an erection?	Very low 1	Low 2	Moderate 3	High 4	Very high 5
2. When you had erections with sexual stimulation, how often were your erections hard enough for penetration?	Almost never or never 1	A few times (much less than half the time) 2	Sometimes (about half the time) 3	Most times (much more than half the time) 4	Almost always or always 5
3. During sexual intercourse, how often were you able to maintain your erection after you had penetrated your partner?	Almost never or never 1	A few times (much less than half the time) 2	Sometimes (about half the time) 3	Most times (much more than half the time) 4	Almost always or always 5
4. During sexual intercourse, how difficult was it to maintain your erection to completion of intercourse?	Extremely difficult 1	Very difficult 2	Difficult 3	Slightly difficult 4	Not difficult 5
5. When you attempted sexual intercourse, how often was it satisfactory for you?	Almost never or never 1	A few times (much less than half the time) 2	Sometimes (about half the time) 3	Most times (much more than half the time) 4	Almost always or always 5

**Total Score:** \_\_\_\_\_

1-7: Severe ED    8-11: Moderate ED    12-16: Mild-moderate ED    17-21: Mild ED    22-25: No ED

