## Appendix F: 6-item Female Sexual Functionality Index

### FSFI-6 Questionnaire

How would you rate your level (degree) of sexual desire or interest?

Very high	High	Moderate	Low	Very low or none at all
5	4	3	2	1

How would you rate your level of sexual arousal ("turn on") during sexual activity or intercourse?

No sexual activity	Very high	High	Moderate	Low	Very low or none at all
0	5	4	3	2	1

How often did you become lubricated ("wet") during sexual activity or intercourse?

No sexual activity	Almost always or always	Most times	Sometimes	A few times	Almost never or never
0	5	4	3	2	1

When you had sexual stimulation or intercourse, how often did you reach orgasm?

No sexual activity	Almost always or always	Most times	Sometimes	A few times	Almost never or never
0	5	4	3	2	1

How satisfied have you been with your overall sexual life?

Very satisfied	Moderately satisfied	About equally satisfied and dissatisfied	Moderately dissatisfied	Very dissatisfied
5	4	3	2	1

How often did you experience discomfort or pain during vaginal penetration?

Did not attempt intercourse	Almost never or never	A few times	Sometimes	Most times	Almost always or always
0	5	4	3	2	1

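### The IIEF-5 form has no answer for sexual inactivity, FSFI-6 codes it 0 on four of six items, and Section 12.5.2 has no rule for inactive respondents, so the planned means mix activity with function

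*Combined protocol and SAP*

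**What the plan says.** Section 10.3 places sexual function among the exploratory outcomes: "To assess sexual function, we will use gender-specific questionnaires", namely IIEF-5 for men and FSFI-6 for women. Section 1.2 lists longitudinal functional outcomes and HRQOL under the secondary objectives.

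Appendix E prints the IIEF-5 with the recall window "Over the past 6 months". All five items are coded 1 to 5. Item 1, "How do you rate your confidence that you could get and keep an erection", can be answered by anyone. Item 2, "When you had erections with sexual stimulation, how often were your erections hard enough for penetration", presupposes erections with stimulation. Items 3 and 4 presuppose intercourse, and item 5, "When you attempted sexual intercourse, how often was it satisfactory for you", presupposes an attempt. No item has a zero or an inactivity choice. The severity bands under the form run from 1 to 25, and the lowest is 1 to 7.

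Appendix F gives "No sexual activity" the code 0 on the arousal, lubrication and orgasm items, and "Did not attempt intercourse" the code 0 on the pain item. Desire and satisfaction are coded 1 to 5 for every woman.

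For HRQOL, Section 12.5.2 states that "we will calculate the mean and standard deviations of each of the individual indices at baseline and every 3 months", and adds differences between baseline, the time of cCR and last follow-up. It has no rule for inactive respondents or blank items, and Appendices E and F have none either. Appendix D, by contrast, prints a missing-item rule for the stoma scale.

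**The concern.** A man with no sexual activity in the recall window has no fitting answer to items 2 to 5. He may circle the lowest code, answer item 2 on its merits, or leave items blank, and each choice gives a different total or none. A woman in the same position has a fitting answer, but it scores as very low function. On the pain item, not attempting intercourse (0) ranks below the worst pain answer (1).

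Sections 2.1 and 2.2.1 cite sexual dysfunction after TME as part of the reason for organ preservation, so readers will look at these scores. The timing matters too. Time 0 falls about 4 to 12 weeks after some 4 months of chemotherapy, so a 6-month recall at that visit covers most or all of the chemotherapy period, and the time of cCR is one of the planned comparison points. If activity changes over treatment, a change in the mean could be read as a change in function. With at most 37 patients split by sex across two instruments, a few inactive respondents can move a mean.

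**Working it through.** **Inputs from the documents.** IIEF-5: five items coded 1–5; bands 1–7, 8–11, 12–16, 17–21 and 22–25 (Appendix E). FSFI-6: six items, four with a 0 code for inactivity, and desire and satisfaction coded 1–5 (Appendix F). Inactivity rates and mean scores are not given; those used in steps 4 and 5 are assumptions.

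**1. IIEF-5 range against the printed bands.** The bands imply totals from 1 to 25. The printed codes give a minimum of 5 × 1 = 5 and a maximum of 5 × 5 = 25, so the lower limit of 1 is not reproduced. A 0 choice on items 2–5 would give 1 + 4 × 0 = 1 up to 25, which does match the bands.

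**2. What an inactive man can score.**
- Items 2–5 all marked 1: item 1 + 4 = 5 to 9. This is the severe band if confidence is 1–3 (totals 5–7) and the moderate band if it is 4–5 (totals 8–9).
- Item 2 answered on its merits, items 3–5 marked 1: item 1 + item 2 + 3 = 5 to 13, reaching the mild-moderate band.
- Items 2–5 blank and the form summed anyway: item 1 alone = 1 to 5, always in the lowest band.
- Items 2–5 blank and the form left unscored: no total, and he drops out of the mean.

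**3. What an inactive woman scores.** Desire (1–5) + satisfaction (1–5) + 4 × 0 = 2 to 10 of 30. A woman with no inactivity answer scores 6 × 1 = 6 to 6 × 5 = 30.

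**4. Effect on the IIEF-5 mean if inactive men are scored.** With active mean A, inactive score I and inactive share q, the mean is (1 − q)A + qI. When q rises by d and A and I stay fixed, the mean falls by (A − I) × d. Assume A = 22:

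| Inactive score I | d = 0.20 | d = 0.30 |
|---|---|---|
| 5 | 17 × 0.20 = 3.4 | 17 × 0.30 = 5.1 |
| 9 | 13 × 0.20 = 2.6 | 13 × 0.30 = 3.9 |

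The range is 2.6 to 5.1 points. With A = 20 and d = 0.30, it is 11 × 0.30 = 3.3 (I = 9) to 15 × 0.30 = 4.5 (I = 5).

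**5. The same for FSFI-6.** Assume an active mean of 22 and an active share falling from 80% to 50%. With I = 2, the mean goes from 0.8 × 22 + 0.2 × 2 = 18.0 to 0.5 × 22 + 0.5 × 2 = 12.0, a fall of 6.0. With I = 10, it goes from 19.6 to 16.0, a fall of 3.6.

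**6. If inactive men are not scored.** Step 4 no longer applies. The mean covers only men who completed the form, and the problem is selection.

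**The case against.** Three stronger readings are tempting, and the documents do not support them.

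- A reader might infer that every inactive man is classed as having severe dysfunction. Step 2 shows totals of up to 9, or 13 if item 2 is answered on its merits. Section 12.5.2 also plans no report by severity band, so a misclassification by band is not a planned result.
- A reader might infer that FSFI-6 scores inactive women 0. Four items are 0, but the total is 2 to 10 and still varies with desire and satisfaction.
- A reader might infer that the means measure activity instead of function. They mix the two, and where inactive men go unscored the effect is selection.

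The band mismatch is also weaker evidence than it looks. Appendix G prints a lowest I-PSS band starting at 1 although that total can be 0, so loosely printed lower limits occur elsewhere. The mismatch is real, but it does not prove that a 0 choice was intended. The publications cited for the instruments may contain scoring rules that are not visible here.

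Treating men and women differently biases no planned comparison, because the two indices are summarised separately. The size of any shift rests entirely on assumed inputs.

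Active-only means carry their own bias: they condition on a post-treatment variable, and patients who stop because of treatment-related dysfunction leave the average. That rules out replacing the all-patient summary with them, but not reporting both.

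What stands is that the IIEF-5 form has no inactivity answer, FSFI-6 scores inactivity as low function, and the plan has no rule for either.

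**Conclusion.** The point holds as a low-priority improvement. Followed as written, Section 12.5.2 produces all-patient means and differences in which sexual activity and sexual function cannot be separated, or an IIEF-5 mean over a selected subset if inactive men leave items blank. The score ranges in steps 1 to 3 follow from the printed forms alone; the FSFI-6 range of 2 to 10 assumes that all four inactivity codes are used. The 2.6 to 5.1 point fall for IIEF-5 is an illustration that depends on an assumed active mean of 22, an inactive score of 5 to 9, and a 20 to 30 percentage-point rise in the inactive share. The actual shift could be smaller or larger. The consequence is confined to a descriptive exploratory outcome; the cCR analysis, sample size and stopping rules do not change.

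**What to change.** - **Form.** Add one separate tick box to the IIEF-5 in Appendix E for no sexual activity or no attempt at intercourse. Leave the 1 to 5 codes unchanged so that earlier and later forms stay comparable. A 0 code alone would not solve the problem: it would put every inactive man at 1 to 5, always in the lowest band.
- **Section 12.5.2.** For IIEF-5 and FSFI-6, report at each visit the proportion sexually active, and the mean and SD among active patients, alongside and not instead of the planned all-patient summary. State that active-only scores condition on a post-treatment variable. FSFI-6 already records what is needed; the plan should say which answers define a woman as inactive.
- **Blank items.** Do not sum an IIEF-5 form with items 2 to 5 blank into a total. Report it as not scorable, with the count, and without assuming the reason, since a blank may be a refusal.

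The cost is a small form revision and a few sentences in 12.5.2. Numbers per cell will be small. Inactive men who circled 1s on forms already collected cannot be identified, so the proportion active will be incomplete for the earlier IIEF-5 forms.

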## Appendix F: 6-item Female Sexual Functionality Index

### FSFI-6 Questionnaire

How would you rate your level (degree) of sexual desire or interest?

Very high	High	Moderate	Low	Very low or none at all
5	4	3	2	1

How would you rate your level of sexual arousal ("turn on") during sexual activity or intercourse?

No sexual activity	Very high	High	Moderate	Low	Very low or none at all
0	5	4	3	2	1

How often did you become lubricated ("wet") during sexual activity or intercourse?

No sexual activity	Almost always or always	Most times	Sometimes	A few times	Almost never or never
0	5	4	3	2	1

When you had sexual stimulation or intercourse, how often did you reach orgasm?

No sexual activity	Almost always or always	Most times	Sometimes	A few times	Almost never or never
0	5	4	3	2	1

How satisfied have you been with your overall sexual life?

Very satisfied	Moderately satisfied	About equally satisfied and dissatisfied	Moderately dissatisfied	Very dissatisfied
5	4	3	2	1

How often did you experience discomfort or pain during vaginal penetration?

Did not attempt intercourse	Almost never or never	A few times	Sometimes	Most times	Almost always or always
0	5	4	3	2	1

## Appendix G: International Prostate Symptom Score

### International Prostate Symptom Score (I-PSS)

Patient Name: \_\_\_\_\_ Date of birth: \_\_\_\_\_ Date completed: \_\_\_\_\_

In the past month:	Not at All	Less than 1 in 5 Times	Less than Half the Time	About Half the Time	More than Half the Time	Almost Always	Your score
1. Incomplete Emptying How often have you had the sensation of not emptying your bladder?	0	1	2	3	4	5	
2. Frequency How often have you had to urinate less than every two hours?	0	1	2	3	4	5	
3. Intermittency How often have you found you stopped and started again several times when you urinated?	0	1	2	3	4	5	
4. Urgency How often have you found it difficult to postpone urination?	0	1	2	3	4	5	
5. Weak Stream How often have you had a weak urinary stream?	0	1	2	3	4	5	
6. Straining How often have you had to strain to start urination?	0	1	2	3	4	5	
	None	1 Time	2 Times	3 Times	4 Times	5 Times	
7. Nocturia How many times did you typically get up at night to urinate?	0	1	2	3	4	5	
Total I-PSS Score							

**Score:** 1-7: *Mild* 8-19: *Moderate* 20-35: *Severe*

Quality of Life Due to Urinary Symptoms	Delighted	Pleased	Mostly Satisfied	Mixed	Mostly Dissatisfied	Unhappy	Terrible
If you were to spend the rest of your life with your urinary condition just the way it is now, how would you feel about that?	0	1	2	3	4	5	6

### About the I-PSS

The International Prostate Symptom Score (I-PSS) is based on the answers to seven questions concerning urinary symptoms and one question concerning quality of life. Each question concerning urinary symptoms allows the patient to choose one out of six answers indicating increasing severity of the particular symptom. The answers are assigned points from 0 to 5. The total score can therefore range from 0 to 35 (asymptomatic to very symptomatic).

The questions refer to the following urinary symptoms:

Questions	Symptom
1	Incomplete emptying
2	Frequency
3	Intermittency
4	Urgency
5	Weak Stream
6	Straining
7	Nocturia

Question eight refers to the patient's perceived quality of life.

The first seven questions of the I-PSS are identical to the questions appearing on the American Urological Association (AUA) Symptom Index which currently categorizes symptoms as follows:

Mild (symptom score less than or equal to 7)  
Moderate (symptom score range 8-19)  
Severe (symptom score range 20-35)

The International Scientific Committee (SCI), under the patronage of the World Health Organization (WHO) and the International Union Against Cancer (UICC), recommends the use of only a single question to assess the quality of life. The answers to this question range from "delighted" to "terrible" or 0 to 6. Although this single question may or may not capture the global impact of benign prostatic hyperplasia (BPH) Symptoms or quality of life, it may serve as a valuable starting point for a doctor-patient conversation.

The SCI has agreed to use the symptom index for BPH, which has been developed by the AUA Measurement Committee, as the official worldwide symptoms assessment tool for patients suffering from prostatism.

The SCI recommends that physicians consider the following components for a basic diagnostic workup: history; physical exam; appropriate labs, such as U/A, creatine, etc.; and DRE or other evaluation to rule out prostate cancer.

**Appendix H: EuroQOL Group five dimensions Health Questionnaire (EQ-5D)**

**Health Questionnaire**

**English version for the USA**

Under each heading, please check the ONE box that best describes your health TODAY.

**MOBILITY**

- I have no problems walking
- I have slight problems walking
- I have moderate problems walking
- I have severe problems walking
- I am unable to walk

**SELF-CARE**

- I have no problems washing or dressing myself
- I have slight problems washing or dressing myself
- I have moderate problems washing or dressing myself
- I have severe problems washing or dressing myself
- I am unable to wash or dress myself

**USUAL ACTIVITIES** (e.g. work, study, housework, family or leisure activities)

- I have no problems doing my usual activities
- I have slight problems doing my usual activities
- I have moderate problems doing my usual activities
- I have severe problems doing my usual activities
- I am unable to do my usual activities

**PAIN / DISCOMFORT**

[figure not shown]
- I have no pain or discomfort
- I have slight pain or discomfort
- I have moderate pain or discomfort
- I have severe pain or discomfort
- I have extreme pain or discomfort

**ANXIETY / DEPRESSION**

- I am not anxious or depressed
- I am slightly anxious or depressed
- I am moderately anxious or depressed
- I am severely anxious or depressed
- I am extremely anxious or depressed

- We would like to know how good or bad your health is TODAY.
- This scale is numbered from 0 to 100.
- 100 means the best health you can imagine.  
0 means the worst health you can imagine.
- Mark an X on the scale to indicate how your health is TODAY.
- Now, please write the number you marked on the scale in the box below.

YOUR HEALTH TODAY =

## 2. Scoring the EQ-5D-5L descriptive system

This example shows how a health state is described using the EQ-5D-5L descriptive system:

Under each heading, please tick the ONE box that best describes your health TODAY.

MOBILITY	
I have no problems in walking about	
I have slight problems in walking about	
I have moderate problems in walking about	
I have severe problems in walking about	
I am unable to walk about	
SELF-CARE	
I have no problems washing or dressing myself	
I have slight problems washing or dressing myself	
I have moderate problems washing or dressing myself	
I have severe problems washing or dressing myself	
I am unable to wash or dress myself	
USUAL ACTIVITIES (e.g. work, study, housework, family or leisure activities)	
I have no problems doing my usual activities	
I have slight problems doing my usual activities	
I have moderate problems doing my usual activities	
I have severe problems doing my usual activities	
I am unable to do my usual activities	
PAIN/DISCOMFORT	
I have no pain or discomfort	
I have slight pain or discomfort	
I have moderate pain or discomfort	
I have severe pain or discomfort	
I have extreme pain or discomfort	
ANXIETY/DEPRESSION	
I am not anxious or depressed	
I am slightly anxious or depressed	
I am moderately anxious or depressed	
I am severely anxious or depressed	
I am extremely anxious or depressed	

Levels of perceived problems are coded as follows:

	Level 1 is coded as a '1'
	
	Level 2 is coded as a '2'
	
	Level 3 is coded as a '3'
	
	
	
	
	Level 4 is coded as a '4'
	
	
	
	
	Level 5 is coded as a '5'
	

This example identifies the health state '12345'.

### Notes:

- There should be only ONE response for each dimension
- Missing values are preferably coded as '9'.
- Ambiguous values (e.g. two boxes are ticked for a single dimension) should be treated as missing values.
- This example is for the EQ-5D-5L Paper Self-Complete. Instructions for the interview and proxy versions are provided with those instruments.

## 2.1/What is a health state?

Each of the five dimensions comprising the EQ-5D descriptive system is divided into five levels of perceived problems:

- LEVEL 1: indicating no problem
- LEVEL 2: indicating slight problems
- LEVEL 3: indicating moderate problems
- LEVEL 4: indicating severe problems
- LEVEL 5: indicating unable to/extreme problems

A total of 3125 possible health states is defined in this way. Each state is referred to by a 5-digit code. For example, working clockwise from the top of the diagram, state 12345 indicates no problems with mobility, slight problems with washing or dressing, moderate problems with doing usual activities, severe pain or discomfort and extreme anxiety or depression, while state 11111 indicates no problems on any of the five dimensions.

A unique health state is defined by combining one level from each of the five dimensions.

11

[figure not shown]
[figure not shown]
